
**Table 9: Probability of Observing an Adverse Event for Various Event Rates**

N	“True” Event Rate	Probability of Observation (%)	N	“True” Event Rate	Probability of Observation (%)	N	“True” Event Rate	Probability of Observation (%)
15	0.1%	1.5	60	0.1%	5.8	75	0.1%	7.2
	0.5%	7.2		0.5%	26.0		0.5%	31.3
	1.0%	14.0		1.0%	45.3		1.0%	52.9

N	“True” Event Rate	Probability of Observation (%)	N	“True” Event Rate	Probability of Observation (%)	N	“True” Event Rate	Probability of Observation (%)
	2.0%	26.1		2.0%	70.2		2.0%	78.0
	3.0%	36.7		3.0%	83.9		3.0%	89.8
	4.0%	45.8		4.0%	91.4		4.0%	95.3
	5.0%	53.7		5.0%	95.4		5.0%	97.9
	10.0%	79.4		10.0%	99.8		10.0%	>99.9
	15.0%	91.3		15.0%	>99.9		15.0%	>99.9
	20.0%	96.5		20.0%	>99.9		20.0%	>99.9
N	“True” Event Rate	Probability of Observation (%)	N	“True” Event Rate	Probability of Observation (%)	N	“True” Event Rate	Probability of Observation (%)
10	0.1%	1.0	30	0.1%	3.0	40	0.1%	3.9
	0.5%	4.9		0.5%	14.0		0.5%	18.2
	1.0%	9.6		1.0%	26.0		1.0%	33.1
	2.0%	18.3		2.0%	45.5		2.0%	55.4
	3.0%	26.3		3.0%	59.9		3.0%	70.4
	4.0%	33.5		4.0%	70.6		4.0%	80.5
	5.0%	40.1		5.0%	78.5		5.0%	87.1
	10.0%	65.1		10.0%	95.8		10.0%	98.5
	15.0%	80.3		15.0%	99.2		15.0%	99.8
	20.0%	89.3		20.0%	99.9		20.0%	>99.9

### 9.3 Populations for Analyses

The Safety Analysis population for the main study includes all subjects who received one dose of vaccine. Analyses for the primary safety population will include safety reported through the end of the main study. A modified primary safety population analysis will also be performed that excludes safety data collected after subjects receive either the third mRNA-1273 vaccination in the optional substudy or non-study EUA vaccine, if applicable.

The modified intent-to-treat (mITT) population includes all subjects who received one dose of vaccine and contributed both pre- and at least one post-vaccination venous blood samples for immunogenicity testing for which valid results were reported.

In the final analysis, protocol deviations will be reviewed to determine which protocol deviations may affect the analysis. The per protocol (PP) population will then be defined – and this includes all subjects in the mITT subset with the following exclusions:

- Data from all available visits for subjects found to be ineligible at baseline.
- Data from all visits subsequent for the protocol deviations that are considered to affect the science.

- Data from any visit that occurs substantially out of window.

## 9.4 Statistical Analyses

Interim analyses of safety, reactogenicity, and immunologic response data may be done, as needed.

The final analysis will be performed after the final data lock (through Day 394) and clinical study report (CSR) completed when all primary safety endpoint data and all secondary immunogenicity endpoint data are available and received by the SDCC. Any available data from the exploratory immunogenicity endpoints may also be included in the CSR. Remaining exploratory immunogenicity endpoint data may be included in an addendum to the CSR, publication of manuscript(s), or other report(s). Abbreviated analysis plans that describe planned analyses to facilitate dissemination of study data for public health reasons, including manuscript publication(s), will be developed by the SDCC. A full statistical analysis plan (SAP) will be developed by the SDCC and finalized prior to the primary data lock.

### 9.4.1 General Approach

Unless otherwise noted in the SAP, continuous variables will be summarized using the following descriptive statistics: n (non-missing sample size), mean, standard deviation, median, maximum and minimum. The frequency and percentages (based on the non-missing sample size) of observed levels will be reported for all categorical measures.

### 9.4.2 Analysis of the Primary Endpoint(s)

[Section 9.4.4](#) describes the analyses of Safety which is the primary endpoint of this protocol.

### 9.4.3 Analysis of the Secondary Endpoint(s)

Summaries and analysis of immunogenicity data will be presented for the mITT population. If there are protocol deviations which may affect the analysis, a per-protocol (PP) analysis may also be performed.

Seroconversion is defined as a 4-fold increase in antibody titer over baseline.

Seroconversion rates, GMFR and GMT for SARS-CoV-2 as measured by IgG ELISA will be calculated at Days 1 (GMT only) and 57 by cohort and will be summarized graphically. Seroconversion rates, GMFR and GMT will be presented with their corresponding 95% confidence interval (CI) estimates at each timepoint and overall peak GMT, and the pair-wise differences between seroconversion rates by cohort will be summarized by study day along with 95% CIs.

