### **9.4.9 Exploratory Analyses**

Summaries and analysis of immunogenicity data will be presented for the mITT population. If there are protocol deviations which may affect the analysis, a PP analysis may also be performed.

Seroconversion is defined as a 4-fold increase in antibody titer over baseline.

Seroconversion rates, GMFR and GMT for SARS-CoV-2 as measured by IgG, IgA and IgM ELISA, neutralization assay using SARS-CoV-2 pseudovirus and neutralization assay using a live wild-type SARS-CoV-2 will be calculated for specified timepoints by cohort and will be summarized graphically. Seroconversion rates, GMFR and GMT will be presented with their corresponding 95% CI estimates at each timepoint and overall peak GMT, and the pair-wise differences between seroconversion rates by cohort will be summarized by study day along with 95% CI.

Summaries and analysis of cellular assay data will be presented for the mITT population. If there are protocol deviations which may affect the analysis, a PP analysis may also be performed.

The magnitude, phenotype and percentage of cytokine producing S protein-specific T cells will be summarized at each timepoint by vaccination group.

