1. PREFACE

The Statistical Analysis Plan (SAP) for “Phase I, Open-Label, Dose-Ranging Study of the Safety and Immunogenicity of 2019-nCoV Vaccine (mRNA-1273) in Healthy Adults” (DMID Protocol 20-0003) describes and expands upon the statistical information presented in the protocol. This document describes all planned analyses and provides reasons and justifications for these analyses. It also includes sample tables, listings, and figures planned for the final analyses. Regarding the final analyses and Clinical Study Report (CSR), this SAP follows the International Conference on Harmonisation of Technical Requirements for Registration of Pharmaceuticals for Human Use (ICH) Guidelines, as indicated in Topic E3 (Structure and Content of Clinical Study Reports), and more generally is consistent with Topic E8 (General Considerations for Clinical Trials) and Topic E9 (Statistical Principles for Clinical Trials). The structure and content of the SAP provides sufficient detail to meet the requirements identified by the FDA and ICH, while all work planned and reported for this SAP will follow internationally accepted guidelines published by the American Statistical Association and the Royal Statistical Society for statistical practice.

This document contains a review of the study design, general statistical considerations, comprehensive statistical analysis methods for immunogenicity and safety outcomes, and a list of proposed tables and figures. Within the table, figure, and listing mock-ups ([Appendix 1](#), [Appendix 2](#), and [Appendix 3](#)), references to CSR sections are included. The reader of this SAP is encouraged to also review the study protocol for details on conduct of the study and the operational aspects of clinical assessments.

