8.2. Secondary Immunogenicity Analyses

Summaries and analysis of immunogenicity data will be presented for the mITT population. If there are protocol deviations which may affect the analysis, a per-protocol (PP) analysis may also be performed. If PP population is different than mITT then the PP population will be used in the interim CSR (iCSR).

Seroconversion is defined as a 4-fold increase in antibody titer over baseline. AUC is calculated using the trapezoidal method applied to a serial dilution curve. For samples with an AUC of zero at baseline, fold-rise will be calculated by dividing post-vaccination result by the lowest reported value.

Seroconversion rates, GMFR, GMT or Williams mean of the AUC for SARS-CoV-2 (S-2P and RBD) as measured by IgG ELISA will be calculated at Days 1 (GMT only) and 57 by cohort and will be summarized graphically (log₁₀ scale). Seroconversion rates, GMFR, GMT or Williams mean of the AUC will be presented with their corresponding 95% confidence interval (CI) estimates (using Student's t-distribution) at each timepoint and overall peak GMT/AUC (starting at Table 24 and ending at Table 47 for GMT/Williams mean and starting at Table 114 and ending at Table 137 for GMFR and seroconversion summaries). Graphical displays will include reverse cumulative distribution plots (Figure 4, Figure 5, Figure 6, Figure 7, Figure 8, Figure 9, Figure 10 and Figure 11), individual titer values over time (starting at Figure 12 and ending at Figure 19), geometric mean over time (Figure 24, Figure 25, Figure 26, Figure 27, Figure 28, Figure 29, Figure 30 and Figure 31) and distributions of responses over time (starting at Figure 48 and ending at Figure 71). Note only endpoint titer values will be reported in the iCSR.

Individual immunogenicity responses are shown in Listing 8.

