Neutralization assays using SARS-CoV-2 pseudovirus neutralization assay (PsVNA) or a wild-type SARS-CoV-2 plaque reduction neutralization test (PRNT) will be run using serial dilutions. ID₅₀ and ID₈₀ will be calculated for PsVNA data using a 5-parameter logistic regression model. ID₅₀ and ID₈₀ will be summarized by group using the geometric mean and 95% CI (using Student's t-distribution) (starting at Table 48 and ending at Table 59). Table 60, Table 61, Table 62 and Table 63 show the day 43 GM summaries of the PsVNA assay at day 43 of the 614D variant. Similarly, for PRNT data, PRNT₈₀ will be calculated using a 5-parameter logistic model. PRNT₈₀ will be summarized using a geometric mean and 95% CI (Table 64, Table 65, Table 66, Table 67, Table 68 and Table 69). Neutralization endpoints will also be displayed graphically on a log₂ or a log₁₀ scale. Similar methods will be used to summarize all additional neutralization assays performed (nanoluciferase-based live virus high throughput neutralization assay, nLuc HTNA, and 2 versions of a live virus focus-reduction neutralization test, FRNT and FRNT-mNG) (starting at Table 70 and ending at Table 95). Graphical displays for PsVNA will include individual titer values over time (Figure 20, Figure 21, Figure 22, and Figure 23), geometric mean over time (Figure 32, Figure 33, Figure 34, and Figure 35) and distributions of responses over time (starting at Figure 72 and ending at Figure 83). Graphical displays for PRNT, nLuc-HTNA, FRNT and FRNT-mNG will include geometric mean over time (starting and Figure 36 and ending at Figure 47) and distributions of responses over time (starting at Figure 84 and ending at Figure 103).

Individual immunogenicity responses are shown in Listing 8.

Spearman correlation between various binding and neutralization assays will be assessed starting at Figure 104 and ending at Figure 115.

Summaries and analysis of cellular assay data will be presented for the mITT population. If there are protocol deviations which may affect the analysis, a PP analysis may also be performed. If PP population is different than mITT, then the PP population will be used in the interim CSR.

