9.3.1. Solicited Events and Symptoms

Systemic solicited adverse events were collected pre-vaccination, and systemic and local solicited adverse events were collected 30 minutes post-vaccination and then daily for 7 days after each vaccination and graded on a scale of 0 (absent), 1 (mild), 2 (moderate) and 3 (severe). Systemic events include: fatigue, headache, myalgia, arthralgia, nausea, chills and fever. Local events include: pain at injection site, erythema, and induration.

The proportion of subjects reporting at least one solicited adverse event will be summarized for each solicited adverse event, any systemic symptom, any local symptom, and any symptoms. The 95% CI calculated using Clopper-Pearson methodology from a binomial distribution (SAS Proc Freq with a binomial option) will be presented (Table 144, Table 145, and Table 146).

For each systemic and local event, any systemic event, any local event, and any solicited event, the maximum severity over 7 days after each vaccination will be summarized for the Safety population. The number and percentage of subjects reporting each event will be summarized by the maximum severity and treatment group, separately for each vaccination and over all vaccinations (Table 147, Table 148, Table 149, Table 150, Table 151, and Table 152). For each event the denominator is the number of subjects with non-missing data for the specific event.

The number of subjects reporting a solicited adverse event will be summarized for each day post vaccination for each vaccination and for all vaccinations combined both in a summary table starting at Table 153 and ending at Table 212 and graphically in a bar chart (Figure 122, Figure 123, Figure 124, Figure 125, Figure 126, and Figure 127).

The mean, standard deviation, median, minimum and maximum duration of solicited events will be summarized (Table 213, Table 214, Table 215).

Day of solicited symptom onset will be summarized graphically (starting at Figure 128 and ending at Figure 139).

Solicited adverse events by subject will be presented in listings (Listing 10 and Listing 11) and graphically (starting at Figure 140 and ending at Figure 175).

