14. TECHNICAL DETAILS

SAS version 9.4, R 3.6.2 and PRISM v8.2.0 or above will be used to generate all tables, figures and listings.

**15. SUMMARY OF CHANGES IN THE CONDUCT OF THE STUDY
OR PLANNED ANALYSES**

Not Applicable.

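### The SAP omits the pairwise seroconversion differences promised in the protocol without recording a change, and names a Student's t interval that does not work for seroconversion rates

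*Protocol*

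**What the plan says.** **Protocol.** Section 9.4.3 plans seroconversion rates, GMFR and GMT by cohort with 95% intervals, and adds that "the pair-wise differences between seroconversion rates by cohort will be summarized by study day along with 95% CIs". Section 9.4.9 extends this to IgG, IgA and IgM ELISA and to both neutralization assays: "the pair-wise differences between seroconversion rates by cohort will be summarized by study day along with 95% CI".

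**SAP text.** The preface states: "This document describes all planned analyses and provides reasons and justifications for these analyses". Sections 8.2 and 8.3 repeat the per-cohort summaries up to the overall peak, and stop there. No between-cohort difference is mentioned. In 8.2 the interval for seroconversion rates, GMFR, GMT and Williams means alike is given as "corresponding 95% confidence interval (CI) estimates (using Student's t-distribution"); 8.3 uses the same method. By contrast, SAP 9.3.1 specifies an exact method for solicited events: "The 95% CI calculated using Clopper-Pearson methodology from a binomial distribution".

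**SAP tables.** The relevant outputs are those "starting at Table 114 and ending at Table 137 for GMFR and seroconversion summaries". The printed shells (Tables 114 and 126) have one column per dose plus a pooled column for the age stratum. Their rows give n, GMFR and the 4-fold-rise percentage with intervals. There is no row or column for a difference. For neutralization, SAP 8.3 says that the ID50 and ID80 values "will be summarized by group using the geometric mean and 95% CI", and the shells show no seroconversion rate. There are no IgA or IgM shells.

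**Record of changes.** SAP section 15, "SUMMARY OF CHANGES IN THE CONDUCT OF THE STUDY" or planned analyses, is marked as not applicable.

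**The concern.** There are two separate defects.

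First, an estimate that the protocol promises for the secondary endpoint would not be produced, and nothing on file says whether that was a decision or an oversight. A SAP may narrow a protocol's plan, but section 15 is the place to say so.

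Second, the SAP attaches to seroconversion rates an interval built for means of roughly normal data. With 10 or 15 subjects and high response rates, it fails where it is most likely to be used. A cohort in which everyone responds would be reported with no uncertainty at all, and a cohort with one non-responder would have an upper limit above 100%.

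**Working it through.** **Inputs.** Cohort sizes are 15 per dose at 18-55 years and 10 per dose at 56-70 and at 71 or over (Protocol Table 1). Cohorts 6, 9 and 13 were not enrolled, which leaves 10 cohorts. Neither document gives a precision figure for seroconversion, so there is none to reproduce, and no expected rate is stated. The counts below are illustrative.

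**Number of differences covered by the protocol wording.** All pairs of 10 cohorts: 10 x 9 / 2 = 45. Within age stratum, with 4, 3 and 3 doses: 6 + 3 + 3 = 12.

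**Student's t interval on 0/1 data.** With p = x/n, the interval is p +/- t(0.975; n-1) x sqrt[p(1-p)/(n-1)].
- 15/15 and 10/10: p(1-p) = 0, so the interval is 100-100%.
- 14/15: sqrt(0.0622/14) = 0.0667; times 2.145 = 0.143; 93.3 +/- 14.3 gives 79.0-107.6%.
- 9/10: sqrt(0.09/9) = 0.10; times 2.262 = 0.226; 90 +/- 22.6 gives 67.4-112.6%.

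**Clopper-Pearson for the same counts.** At full response the lower limit is 0.025^(1/n).
- 15/15: 78.2-100%.
- 10/10: 69.2-100%.
- 14/15: 68.1-99.8%.
- 9/10: 55.5-99.7%.

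**Coverage at an assumed true rate of 95%.** The t interval contains the truth 53.6% of the time at n = 15 and 40.1% at n = 10. Clopper-Pearson gives 99.5% and 98.8%. Nearly all of the shortfall is the full-response outcome, which has probability 0.95^15 = 46.3% or 0.95^10 = 59.9% and yields a single point at 100%.

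**What the restored differences would look like (Newcombe interval).** At full response the Wilson lower limit is n/(n + 1.96^2).
- 15/15 v 15/15: 15/18.84 = 0.796, so the difference is 0 with limits of +/-20.4 points.
- 10/10 v 10/10: 10/13.84 = 0.722, so the limits are +/-27.8 points.
- 15/15 v 13/15: difference 13.3 points, limits -9.2 to +37.9.

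The planned cohort sizes are used throughout because the mITT definition (Protocol 9.3, SAP 6.2.1) requires one dose and at least one valid post-vaccination sample. The four subjects without a second dose (note to Protocol Table 13) are therefore not removed by definition; smaller counts would be a per-protocol scenario.

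**The case against.** **The trial is descriptive.** Protocol 9.1 disclaims any hypothesis test, cohorts were enrolled in sequence without randomization (6.3.2), and SAP 6.7 plans no multiplicity adjustment. That is true, but the protocol promised the differences as estimates on that same footing.

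**The reader can rebuild the comparison.** The tables give n and percentages. SAP 8.2 also plans reverse cumulative distributions, individual titers, geometric means over time and distributions by group, and Listing 8 holds individual results. This stands, and it limits the consequence. It does not replace the promised output or the missing section 15 entry.

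**Rate differences may say little.** If nearly everyone responds, they will be close to zero with wide limits, as shown above. That would be a reason to drop them on record.

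**The Student's t wording may be loose drafting** meant only for GMT and GMFR. That is possible. The SAP prints no formula, so the t interval on 0/1 data is the literal reading. But seroconversion rates are in the list and no binomial method is named for them.

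**Stronger readings that the documents do not support.**
- A reader might infer that the SAP removed a between-dose titer comparison. It did not: neither document ever planned a GMT ratio.
- A reader might see the same defect in the substudy, where Protocol 12.5 and 12.7.2 compare the 25 and 50 mcg responses with 100 mcg while 12.11.7 lists per-cohort summaries. Protocol 12.11.4 leaves the full substudy SAP still to be written, so no omission can be established yet.
- Nothing shows that the omission was deliberate.

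**Conclusion.** Both defects hold for the main study and should be corrected. The omission follows from setting Protocol 9.4.3 and 9.4.9 beside SAP 8.2, 8.3, 15 and the table shells, and needs no assumption. For IgA, IgM and neutralization the gap is wider, because the SAP tables contain no seroconversion rates from which to form a difference.

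The interval defect rests on reading the Student's t wording as written. Its size depends on the observed rates, which the documents do not give. At full response the stated method reports 100-100% where an exact interval reaches down to 78.2% (n = 15) or 69.2% (n = 10). With one non-responder its upper limit is 107.6% or 112.6%. The coverage figures of 53.6% and 40.1% assume a true rate of 95%.

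The damage is an unreported estimate, an unrecorded departure from the protocol and misleading intervals. GMT and GMFR summaries, for which Student's t on the log scale is suitable, are unaffected.

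**What to change.** 1. **Interval method.** In SAP 8.2 and 8.3, limit Student's t to log-scale GMT, GMFR and Williams means. For seroconversion rates, name Clopper-Pearson, as in SAP 9.3.1, or a score interval.
2. **Differences.** Restore the Day 57 IgG seroconversion differences in the fold-rise tables with a Newcombe interval. If only the 12 within-stratum pairs are kept out of 45, or if IgA, IgM or neutralization differences are not produced, record and explain that in section 15.
3. **Optional, not the correction of an error.** Add descriptive Day 57 IgG GMT ratios of each dose to 100 mcg within age stratum (3 + 2 + 2 = 7 per antigen), labelled as non-randomized and unadjusted. At an assumed log10 SD of 0.3, the 95% limits are the ratio multiplied and divided by 1.68 (15 per cohort) or 1.91 (10 per cohort). For SDs of 0.2-0.5 the factors run 1.41-2.37 and 1.54-2.95. The documents give no SD.

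**Cost.** The first two items need revised wording, a few added table rows and a section 15 entry for anything left out, all from data the trial already collects and with no hypothesis tests. Producing the IgA, IgM and neutralization differences, if wanted, would need new tables. The downside of item 3 is more unadjusted estimates with wide intervals.

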### 9.4.4 Safety Analyses

Summaries and analysis of safety data will be presented for the Safety Analysis Population.

Solicited AEs will be summarized by severity for each day post vaccination (Days 1-8) and as the maximum severity over all 8 days. Additionally, solicited AEs will be analyzed by taking the most severe response over the follow-up period, dichotomizing into a binary variable (none versus mild, moderate, or severe) and using standard techniques, such as exact confidence

intervals (CI), to summarize the proportion of subjects reporting each symptom, any application site symptom, and any systemic symptom.

Unsolicited non-serious AEs will be collected from the time of first vaccination through 28 days after the second vaccination. Unsolicited AEs will be coded by MedDRA for preferred term and system organ class (SOC). SAEs, Protocol Specified AESIs, MAAEs, and NOCMCs will be collected from the time of first vaccination through the end of the study (Day 394). The numbers of SAEs and MAAEs will be reported by detailed listings showing the event description, MedDRA preferred term and SOC, relevant dates (vaccinations and AEs), severity, relatedness, and outcome for each event. Non-serious unsolicited AEs will be summarized as number and percentage of subjects reporting at least one event in each MedDRA preferred term and SOC, cross tabulated by severity and relationship to study product. Additionally, the proportion of subjects and exact 95% CIs of AEs in aggregate and by MedDRA categories will be computed.

Clinical laboratory data will be summarized by severity for each visit, and as the maximum over all post-vaccination visits. Graphical presentations may include box plots and shift plots.

